2. PROTOCOL SYNOPSIS

Name of Sponsor:	[name].
Name of Investigational Product:	Spironolactone
Name of Active Ingredient:	Spironolactone
Study Title:	A randomized open label pilot trial of spironolactone versus prednisolone in corticosteroid-naïve boys with DMD
Study Number:	N=24
Sponsor-Principal Investigator:	[name].
Clinical Study Phase:	Pilot Study
Number of Centers:	Four to seven centers
Study Duration:	6 months. Subjects will undergo strength and functional testing at screening (Day -14 to 0) and monthly electrolyte testing. Follow up strength and functional testing will occur on Days 90 and 180. After 6 months of treatment, all subjects will be offered standard glucocorticoid therapy based on their local clinic's standard of care or continued dosing on the medication taken during the trial if there is clear established efficacy.
Study Design:	Randomized, open-label, pilot clinical trial of spironolactone suspension versus oral prednisolone
Study Objectives:	To determine if 6 months of treatment with either spironolactone or a standard clinical dose of corticosteroids results in equivalent improvement in time to complete the 100 meter timed test (100M). To assess the safety of spironolactone treatment in the steroid naïve DMD population.
Patient Population:	Inclusion Criteria: 
• Duchenne muscular dystrophy (DMD) patients ≥ 4 to ≤ 7 years of age• Clinical features of DMD that include proximal predominant weakness and/or gait disturbance• Presence of a truncating mutation of the DMD gene in the patient or an affected male relative OR a muscle biopsy that demonstrates $<5\%$ dystrophin in the patient or an affected male relative• Normal left ventricular ejection fraction by screening echocardiogram• Ability to cooperate for testing

	
• No prior treatment with glucocorticoids or vamorolone• No concomitant experimental therapies
	
Exclusion Criteria:
 
• Subject amenable to or currently being treated with eteplirsen, golodirsen, casimersen, or viltolarsen• Hyperkalemia at screening• History of or ongoing renal failure (elevated creatinine, oliguria, anuria)• Hypersensitivity to spironolactone (rash, respiratory distress, arrhythmia, numbness or tingling of extremities)• Current treatment with an ACEi• Severe peptic ulcer disease or recent gastrointestinal perforations
Study Procedures:	Subjects will receive either prednisolone or spironolactone. Strength and functional testing will occur at screening (Day -14 to 0) and at 90 and 180 days after initiation.
Study Outcomes:	
Primary:
 
• Time to complete the 100 meter timed test (100M) 
Secondary:
 
• Muscle strength as measured by dynamometry score, a composite score made up of values from maximum voluntary isometric contraction testing of the flexors and extensors of the elbows and knees, as measured in kilograms of force.• North Star Ambulatory Assessment (NSAA), a functional scale validated in the DMD population• 4-stair climb• Time to arise from floor 
Exploratory:
 
• Safety measures• Biomarker studies
Sample Size:	A total of 24 subjects are expected to be enrolled in this trial, with 12 randomized to each treatment group. 
• Treatment Group 1: Spironolactone 1 mg/kg/day (n=12 subjects)• Treatment Group 2: Prednisolone 0.75 mg/kg/day (n=12 subjects) or weekend dosing per the sites standard of care

Statistical Analysis:	
Age-corrected 100M will be considered as the primary outcome, and will be evaluated using a two-one-sided t-test to test equivalency between treatment arms in the change from baseline to 6 months. In addition, repeated measures ANOVA will be used to determine whether the trajectory across all three time points (baseline, 3mo, 6mo) differs by treatment group. Strength testing/dynamometry, NSAA, 4-stair climb, and time to arise from floor scores will be secondary outcomes, and will also be compared by treatment group using repeated measures ANOVA. Biomarkers studies will be considered exploratory outcomes.
 
Power: Prior studies evaluating the 100m walk test among patients with DMD have shown an average change over 6 months of -2.9 ±7.8. An effective sample size of 10 patients per group will provide 80% power to declare equivalency with an equivalence margin of ±10.6.

Long-term follow-up:	All adverse events will be followed until resolution or stabilization.

3. LIST OF ABBREVIATIONS AND DEFINITIONS OF TERMS

The following abbreviations and specialist terms are used in this study protocol.

Table 1 Abbreviations and Specialist Terms

Abbreviation	Definition
ACEi	Angiotensin Converting Enzyme Inhibitor
DMD	Duchenne muscular dystrophy
MDA	Muscular Dystrophy Association
MR	Mineralocorticoid Receptor
NSAA	North Start Ambulatory Assessment
Sponsor-Investigator	Nationwide Children's Hospital Principal Investigator
Principal Investigator	Site Principal Investigators

5. INTRODUCTION: BACKGROUND INFORMATION AND SCIENTIFIC RATIONALE

5.1 Background

We propose a randomized open label pilot clinical trial of spironolactone versus prednisolone in corticosteroid-naïve boys ages 4-7 years old. The glucocorticoids prednisolone and deflazacort have been shown to improve muscle strength and to prolong ambulation in boys with DMD⁸. The effects in mdx mice are controversial and neither has clearly been shown to reverse skeletal muscle pathology in human disease or in animal models. The mechanism of action of corticosteroids is unclear, but several have been suggested, including stabilization of muscle membranes, diminishing the activation of calcium dependent proteases (and thus a decrease in subsequent myofiber degeneration), and decreasing intramuscular fibrosis. Corticosteroids have a significant side effect profile that includes obesity, cushingoid features, osteoporosis, and

behavioral disturbances. These side effects become pronounced after what may be a decade or more of treatment in boys with DMD, and often are the cause of cessation of therapy or subtherapeutic dosing in the shorter term.

Spironolactone is an aldosterone antagonist primarily used as a potassium sparing diuretic. However, it also has anti-androgen effects, and is used to treat a variety of conditions, including hirsutism in women. Its side effect profile is well known, and includes gynecomastia and hyperkalemia. It is widely used, however, in the pediatric population, with limited side effects⁹. A recent study by [name], a Co-Investigator, evaluated the effect of spironolactone treatment in the mdx mouse (the standard animal model of DMD) and mdx:utr^{+/}- mouse also lacking 1 copy of utrophin since these mice demonstrate more severe histopathologic changes (including markedly increased fibrosis)¹⁰. In several published studies, a combined treatment with the angiotensin converting enzyme (ACE) inhibitor lisinopril and mineralocorticoid receptor (MR) antagonist spironolactone reduces ongoing skeletal muscle damage and improves muscle function in DMD mouse models¹⁰⁻¹². These include improvements of cardiac, limb, and diaphragm function approaching 80% of normal following early treatment (at 4 weeks after birth), an extraordinary effect in comparison to many other preclinical studies of compounds that have been tested in humans – besting, for example, the protection provided by prednisone in the mdx mouse¹¹. These preclinical results have already been translated into a published double-blind, placebo controlled clinical trial with the MR antagonist eplerenone showing efficacy in primary cardiac outcomes in DMD patients¹³. Due to the inclusion criteria for this trial, many patients were already nonambulatory and skeletal muscle function was not assessed. A second non-inferiority double-blind trial comparing specific and non-specific MR antagonists with primary cardiac outcomes is currently underway.

Spironolactone and lisinopril target the mineralocorticoid receptor directly and indirectly, respectively, through the renin-angiotensin-aldosterone system. Treatment with lisinopril alone improves histopathology, but cannot recapitulate improvements in skeletal muscle function of dystrophic mice after combined treatment with spironolactone¹⁴. [name] has recently shown that the MR is present in both mouse and human skeletal muscle fibers¹⁵. Treatment of normal human myotubes with aldosterone results in a large number of gene expression changes, supporting MR functions as a nuclear hormone receptor in skeletal muscles¹⁵. Treatment of dystrophic mice also demonstrates increased muscle membrane stabilization as demonstrated by laser injury assays¹⁶.

We have now also shown that infiltrating myeloid cells clustered in damaged areas of dystrophic mouse skeletal muscles have the capacity to produce the natural ligand of the MR, aldosterone¹⁶, which in excess is known to exacerbate tissue damage. Aldosterone synthase protein levels are increased in leukocytes isolated from dystrophic mouse muscles compared with controls and local aldosterone levels in dystrophic skeletal muscles are increased, despite normal circulating

levels. 11 β -HSD2, the enzyme that inactivates glucocorticoids to increase MR selectivity for aldosterone, is also increased in dystrophic mouse muscle tissues¹⁶. These data suggest MR activation is in excess of physiological need, likely contributes to the pathology of muscular dystrophy, and explains the likely mechanism of preclinical efficacy of MR antagonists in skeletal muscles and heart. Since DMD patients have even more muscle inflammation than dystrophic mice, this approach has the potential to be even more efficacious in patients.

The pilot trial we propose will directly answer the question of whether spironolactone is as efficacious as prednisolone over 6 months of treatment in young patients (age ≥ 4 to ≤ 7 years) with DMD, as judged by the age-corrected 100 meter timed test and by dynamometry scores derived maximum voluntary isometric contraction testing of selected muscles and the time to climb 4 stairs. For steroid-naïve patients, this could delay institution of prednisolone therapy – considered the standard of care – for up to 6 months. However, it is important to recognize that not all DMD parents choose for their boys to go on steroids during this age window, and that there is no clear evidence based consensus of when treatment must be initiated. Finally, we note that published data from [name] lab and others demonstrates that prednisolone results in increased cardiac deterioration in the mdx mice, suggesting cardio-toxic effects on dystrophic heart^{11, 17}. Therefore, we feel that delaying onset of steroid therapy is justified for this pilot trial in order to gain meaningful pilot data regarding spironolactone in DMD patients, and note that all subjects will be offered open label prednisolone therapy as a standard of care after completion of the trial. If there is equal or greater efficacy with spironolactone, they may choose to continue on spironolactone.

In this pilot trial we will use prednisolone since it is delivered as an oral suspension. Since the standard of care regimen (daily versus weekend dosing of prednisolone) differs from site to site, each PI will have the discretion to assign subjects to their preferred regimen. Equal efficacy has been shown between daily and weekend dosing regimens¹⁸.

5.2 Rationale

DMD is a devastating disorder of childhood, leading to loss of ambulation by age 12 years, and typically to death between 20 and 30 years. Until recently, the only treatment shown to improve strength and preserve ambulation in DMD patients was the use of glucocorticoids, which are accompanied by significant side effects. Recent developments in gene corrective therapies (such as the exon-skipping oligomer eteplirsen or the nonsense-suppression compound ataluren) represent potential therapies only for those relatively small subsets of patients with mutations that are amenable to that specific corrective mechanism (around 13% and 15% of DMD patients, respectively)¹⁹. We wish to determine whether another commonly used medication, spironolactone, may have similar beneficial effects with a lower side effect profile and be applicable to a wider population of DMD patients.

Our hypothesis for this controlled pilot trial is that spironolactone and prednisolone are of equal efficacy in improving skeletal muscle function over a 6-month period, and that spironolactone will be well tolerated in this patient population.

One outcome is that both drugs demonstrate equal efficacy in motor function. This would then serve as pilot data for a longer term study.

6. OBJECTIVES AND PURPOSE

6.1 Primary Outcome

The primary objective of this trial is to determine whether spironolactone has similar efficacy to glucocorticoids in improving muscle strength in steroid naïve DMD patients. Glucocorticoids are the only medications that have been shown to change the clinical course of Duchenne muscular dystrophy, but have significant side effects (e.g., obesity, cushingoid features, osteoporosis, and behavioral disturbances). Preclinical data suggests a significant protective effect from spironolactone in the mdx and mdx;utrn^{+/−} animal models. We propose a randomized, open-label pilot trial comparing spironolactone to prednisolone.

The primary outcome measure will be the time to complete a 100 meter timed test (100M)²⁰.

6.2 Secondary Outcome

Secondary outcome measures will be Dynamometry score, which is a summation of maximum voluntary isometric contraction test values for knee flexion, knee extension, elbow flexion, and elbow extension; 4-stair climb; North Star Ambulatory Assessment (NSAA); and time to arise from the floor.

6.3 Exploratory Outcome

An exploratory outcome is to assess the safety of delivering spironolactone to the steroid naïve DMD population. Safety data will be monitored on a continual basis throughout the trial by the Principal Investigator and study staff.

Additional exploratory outcomes include biomarker studies.

7. STUDY DESIGN AND ENDPOINTS

7.1 Overall Study Design

The proposed trial will involve 24 subjects with DMD. Because DMD is an X-linked disorder, all subjects will be boys. Subject selection will not exclude anyone on the basis of race or ethnic background.

12 subjects will be randomized to each treatment group as follows:

- **Treatment Group 1:** Spironolactone 1 mg/kg/day (n=12 subjects)
- **Treatment Group 2:** Prednisolone 0.75 mg/kg/day (n=12 subjects) or weekend dosing as per sites standard of care

7.2 Study Population

DMD patients (n =24) will be enrolled in a randomized open label controlled trial of prednisolone (n= 10) versus spironolactone (n = 10) based on inclusion criteria as defined below. Four to seven collaborating centers will participate. Up to 24 subjects (~ 3 at each site) can be enrolled to include a 10% drop-out rate.

Power: Prior studies evaluating the 100m walk test among patients with DMD have shown an average change over 6 months of -2.9 ± 7.8 . An effective sample size of 10 patients per group will provide 80% power to declare equivalency with an equivalence margin of $\pm 10.6^{21}$.

Siblings will be permitted to participate. When sibling participation arises, the randomization will proceed as if they were unrelated.

7.3 Number of Subjects

A total of 24 subjects will be enrolled.

7.4 Dosing Plan

This is a randomized open label controlled pilot trial comparing spironolactone suspension and prednisolone. Medications will be provided by each institutional pharmacy. Each subject will be provided with a 90-day supply of medication. Subjects will be enrolled for a period of 6 months. Specific criteria for administering the drugs are as follows:

Patients fulfilling entry criteria will be enrolled in the trial and receive medication at designated dosing. They will receive either prednisolone 0.75 mg/kg/day, or spironolactone 1 mg/kg/day. Weekend prednisolone dosing as per sites standard of care is an acceptable alternative.

Subjects will be weighed at screening, Month 3, and Month 6. Weight based dose adjustments to the study drug should be made by the Study Doctor.

7.5 Spironolactone Suspension

Carospir® (spironolactone) 25 mg/5ml oral suspension is commercially available as a white to off-white, opaque, banana-flavored suspension and can be stored at room temperature. The product is manufactured by CMP Pharma, Inc. Study drug will be dosed daily at 1mg/kg.

Although spironolactone is commercially available in a suspension, it is NOT therapeutically equivalent to the tablets. The suspension results in 15% to 37% higher serum concentration compared to the tablet. Pediatric dosing is based on experience with tablets and extemporaneously compounded suspension.

7.6 Prednisolone

The Study Doctor at each study site will prescribe their preferred regimen of prednisolone. Daily dosing at 0.75 mg/kg/day or weekend dosing as per sites standard of care is acceptable. Study drug will be provided by the pharmacy at each study site every 90 days. The product is manufactured by Morton Grove Pharmaceuticals. If at any point the drug becomes unavailable from this manufacturer, another manufacturer can be used to obtain the drug until available from Morton Grove Pharmaceuticals.

Prednisolone is available commercially as a 15mg/5ml solution. It can be stored at room temperature. It is a clear solution with a grape odor and flavor. It contains 1.8% alcohol.

7.7 Establish Subject Identification Number

Research subjects will be assigned a randomization number (i.e., 1001, 1002, sequentially) prior to enrollment to facilitate randomization to one of two treatment groups, Spironolactone Treatment Group or Prednisolone Treatment Group. Upon consent, every research subject will be assigned a Subject Identification code. This will be done prior to any research procedures being scheduled, as they will require a Subject ID.

The Subject Identification code is generated as follows:

- 1) 3 letter site identifier
- 2) 2 digit study number
- 3) 3 digit sequential number of all candidates being screened

Example: Subject ID: NCH-01-001

8. STUDY ENROLLMENT AND WITHDRAWAL

24 male DMD subjects, ages ≥ 4 to ≤ 7 years who are steroid naïve will be enrolled in this pilot clinical trial. Subjects will be of any racial or ethnic background. Enrollment will be ongoing. The assessment and full treatment plan will be used for all subjects.

8.1 Subject Inclusion Criteria

Subjects must meet all of the following Inclusion Criteria:

1. Duchenne muscular dystrophy (DMD) patients ≥ 4 to ≤ 7 years of age
2. Clinical features of DMD that include proximal predominant weakness and/or gait disturbance

3. Presence of a truncating mutation of the *DMD* gene in the patient or an affected male relative OR a muscle biopsy that demonstrates <5% dystrophin in the patient or an affected male relative
4. Normal left ventricular ejection fraction by screening echocardiogram
5. Ability to cooperate for testing
6. No prior treatment with glucocorticoids or vamorolone
7. No concomitant experimental therapies

8.2 Subject Exclusion Criteria

Subjects must not meet any of the following Exclusion Criteria:

1. Subject amenable to or currently being treated with eteplirsen, golodirsen, casimersen, or viltolarsen
2. Hyperkalemia at screening
3. History of or ongoing renal failure (elevated creatinine, oliguria, anuria)
4. Hypersensitivity to spironolactone (rash, respiratory distress, arrhythmia, numbness or tingling of extremities)
5. Current treatment with an ACEi
6. Severe peptic ulcer disease or recent gastrointestinal perforations

8.3 Randomization

Nationwide Children's Hospital pharmacy will serve as the lead pharmacy. Randomization will be determined via the lead pharmacy. Subjects at each site will be randomized 1:1 to receive treatment with either prednisolone at 0.75 mg/kg/day (or weekend dosing per sites standard of care) or spironolactone at 1mg/kg/day. Subjects will be assigned treatment sequentially from the provided list. Subjects will not be randomized until the echocardiogram and all lab results are finalized and reviewed by the Study Doctor.

8.4 Baseline Assessment of Endpoints

After obtaining informed consent and completing the registration procedures, baseline subject history data will be collected, including records of all medications and supplements that the subject is taking. The following assessments will be performed to confirm subject eligibility for this trial. Screening tests must be completed prior to treatment administration as described in the study timeline. Screening testing includes the following, which are discussed in detail below:

- 100 meter timed test (100M)
- Strength testing and dynamometry
- North Star Ambulatory Assessment (NSAA)
- 4-stair climb
- Time to arise from floor
- Echocardiogram
- Baseline laboratory testing

The subject and his parents will be aware that his participation may be terminated after any of these screening procedures.

There is no central laboratory for this trial. Site-specific normal lab ranges will be documented in respective sites' regulatory binders. Lab ranges will be provided by each site's laboratory. Laboratory tests with values within the clinically significant range will be repeated during the same visit whenever possible. If the test result returns after the subject leaves the clinic, they will be immediately contacted. Subjects will be asked to return to the outpatient clinic for a repeat test. For non-local subjects, arrangements can be made to have the blood test redrawn in a laboratory close to home or by their primary care physician. If still out of the range and clinically significant, the subject may be terminated from the study following discussion with the Clinical Safety Monitor.

To avoid any confusion for the primary care physician, he or she will be informed (with permission from the subject) of their participation in the trial at the time of enrollment.

8.5 Subject Withdrawal Criteria

Subjects meeting the following criteria will be withdrawn from the trial:

1. Unable to tolerate study medication.
2. Failure to keep an accurate medication log.
3. Failure to keep study appointments.
4. Missing more than 10% of prescribed doses of study medication.*

**If a subject is missing more than 10% of prescribed doses, a discussion about the subject's continuation in the trial will take place between the Principal Investigator and the Sponsor-Investigator.*

Corticosteroids are the standard of care for the treatment of Duchenne muscular dystrophy and have a well-known side effect profile (see section 9.3). Subjects with any Grade 1 or higher (according to the Common Terminology Criteria for Adverse Events (CTCAE) version 4.03 and listed in section 11.1) adverse events that are anticipated and related to prednisolone use, will continue in the trial. Subjects with any Grade 2 or higher adverse events that are anticipated and are possibly, probably or definitely related to spironolactone use will have the study drug held and will be re-challenged in 1 week. If a subject experiences a recurrence of the adverse event, he may be withdrawn after discussion with the Clinical Safety Monitor. Subjects with any Grade 2 or higher adverse events that are unanticipated, may be withdrawn after discussion with the Clinical Safety Monitor. The Principal Investigator will determine a clinically appropriate tapering regimen with respect to assigned study drug and length of time on drug.

Principal Investigators must report all participant withdrawals to the Sponsor-Investigator within 48 hours of learning of the withdrawal. The Sponsor-Investigator will then notify the Clinical Safety Monitor of the withdrawal within 3 business days of the Sponsor-Investigator learning of the withdrawal.

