9. STUDY AGENT

Site pharmacies will dispense spironolactone and prednisolone per the site's standard procedures. In the rare instance of a subject not being able to tolerate prednisolone, an equivalent dose of prednisone may be provided as crushed tablets after approval by the Sponsor-Investigator.

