10.7.1 Long Term Monitoring

All adverse events occurring throughout the subject's participation in the trial through 30 days after the subject's final study visit will be documented and followed until resolution or stabilization. Research staff will contact subjects 30 days after the subject's final study visit to check for any new AEs and to obtain any new information regarding ongoing AEs.

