If a serious adverse event occurs within 30 days after a subject's final study visit and is determined to be unexpected and related to the use of either study drug, that event will be reported to the Reviewing IRB within **3 business days** of the Sponsor-Investigator learning of the determination.

Should a serious adverse event deemed possibly, probably or definitely related to the study agent occur during administration, the study agent will be discontinued, appropriate treatment will be given under medical supervision and the subject will be examined as frequently as necessary thereafter until symptoms cease or stabilize.

All new information and significant noncompliance indicating a new or increased risk or new safety issue as defined in the Reviewing IRB policies will be reported to the Sponsor-

Investigator within **48 hours** of the Principal Investigator learning of the information. The Sponsor-Investigator will report to the Reviewing IRB within **3 business days** of the Sponsor-Investigator's initial receipt of the information. This includes deviations from the protocol that harmed subjects or others or that indicates subjects or others might be at an increased risk of harm.

The Sponsor-Investigator will inform the Clinical Safety Monitor of all serious adverse events regardless of severity, relatedness, or expectedness and of all instances of significant non-compliance impacting patient safety within **48 hours** of the Sponsor-Investigator's initial receipt of the information.

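### Section 8.5 takes boys out of the trial for several drug-related reasons, and no functional test or analysis rule covers a boy who stops drug, so the Month 6 equivalence test would in effect use only boys still in the trial

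*Combined protocol and SAP*

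**What the plan says.** **Leaving the trial.** The list in Section 8.5 opens: "Subjects meeting the following criteria will be withdrawn from the trial". Three of its criteria carry no qualifier: intolerance of study medication, failure to keep an accurate log, and failure to keep appointments. For the fourth, more than 10% of doses missed, a footnote says that a discussion on "continuation in the trial will take place between the Principal Investigator and the Sponsor-Investigator".

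**Adverse events.** The rules in 8.5 differ by arm. Boys with "adverse events that are anticipated and related to prednisolone use, will continue in the trial". Boys with anticipated, related spironolactone events of Grade 2 or higher "will have the study drug held and will be re-challenged in 1 week", and then: "If a subject experiences a recurrence of the adverse event, he may be withdrawn after discussion with the Clinical Safety Monitor". Unanticipated events of Grade 2 or higher may also lead to withdrawal in either arm.

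**Related text elsewhere.** Section 9 provides a substitute for one arm only: "In the rare instance of a subject not being able to tolerate prednisolone, an equivalent dose of prednisone may be provided as crushed tablets". Section 11.3.2 covers a related serious event during administration: "the study agent will be discontinued, appropriate treatment will be given under medical supervision". It goes on to clinical examination and does not say whether the boy stays in the trial.

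**Testing and analysis.** Table 3 and Sections 10.3 to 10.7 place the 100M at screening, Month 3 and Month 6, with no early-termination visit. The contact 30 days after the final visit is "to check for any new AEs and to obtain any new information regarding ongoing AEs". Section 13 tests equivalence on the change from baseline to Month 6 and names no analysis set and no missing-data method.

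**The concern.** A Month 6 change score needs a Month 6 test. A boy who has left has none scheduled, and Section 13 does not say what happens to him in the analysis, so by default he drops out of the primary comparison.

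With 12 boys per arm, one or two absences can move a mean. The exit rules and the substitute product differ by arm, so the losses may not balance. If they do not, and the lost boys differ in outcome, the comparison is biased, in either direction. Bias that makes the arms look more alike matters most here, because it favours the conclusion the trial hopes to reach.

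**Working it through.** **1. The plan's own figure.** Inputs from Sections 7.2 and 13: SD 7.8, margin 10.6, 10 per group, 80% power. Alpha and the true difference are not stated; I take 0.05 per one-sided test and zero.
- The test declares equivalence when |d| + t × SE < 10.6.
- SE = 7.8 × √(2/10) = 3.49, and t (18 df, 0.95) = 1.734.
- Exact power is 79.8%, which reproduces the 80%. At 0.025 per side it would be 63.9%, so 0.05 is the reading that fits.
- Drop-out: 10/0.9 = 11.1, hence 12 per arm. With all 12 per arm analysed, power is 88.6%.

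**2. Loss in the spironolactone arm only.** Assume that k of 12 boys leave, that their mean change is D worse than that of the stayers, and that the true difference among all randomized boys is at the margin. The difference among stayers is then 10.6 − k × D/12. False equivalence with no loss is 5.0%.

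| D | k = 1: shift | k = 1: false equivalence | k = 2: shift | k = 2: false equivalence |
|---|---|---|---|---|
| 3.9 (0.5 SD) | 0.325 | 6.1% | 0.65 | 7.3% |
| 7.8 (1 SD) | 0.65 | 7.3% | 1.30 | 10.2% |
| 15.6 (2 SD) | 1.30 | 10.4% | 2.60 | 18.6% |

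If the lost boys are better by 1 or 2 SD, the figures fall to 3.3% or 2.1% (k = 1) and 2.2% or 0.8% (k = 2).

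**3. How likely such patterns are.** With independent 10% loss per boy, the chances that an arm loses none or exactly one are 0.282 and 0.377.
- Exactly 1 v 0 in the stated direction: 0.377 × 0.282 = 0.106. This is 1 of 24 boys, or 4% overall.
- Two or more in a given arm: 1 − 0.282 − 0.377 = 0.341. With none lost in the other arm: 0.341 × 0.282 = 0.096.

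**4. Loss in both arms.** Assume 10% loss in each arm with the same gap D in each. For i boys lost on spironolactone and j on prednisolone, the stayers' difference is 10.6 − (i − j) × D/12. Averaged over the binomial loss patterns, false equivalence is 5.1%, 5.6% and 7.3% for D = 0.5, 1 and 2 SD. When i = j there is no shift.

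**5. Testing boys off drug.** Suppose instead that the on-drug difference is at the margin and that k boys who stop spironolactone revert to the prednisolone mean. The all-randomized difference is 10.6 × 11/12 = 9.72 or 10.6 × 10/12 = 8.83. The all-randomized test then gives about 7.5% (k = 1) or 11% (k = 2) false equivalence, against 5.0% in stayers.

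**6. Requiring both sets to meet the margin** (simulation, 400,000 runs). False equivalence is 5% or less in both the persisting-gap cases (1 and 2 SD) and the reversion cases. Power at zero difference is about 85% (1 lost) or 83% (2 lost), against 89% for all randomized boys alone.

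**The case against.** **The size is modest under an even-handed assumption.** This stands. The 10% drop-out in Section 7.2 is not arm-specific, and step 4 gives little inflation below a 2 SD gap. The larger figures in step 2 need loss in one arm only and in the harmful direction, and 2 SD is about 1.5 times the margin (15.6/10.6). No criterion in 8.5 refers to motor function.

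**A reader might infer that no boy can ever stay in after stopping drug.** The text does not go that far. Missed doses lead to a discussion, adverse-event exits are permissive, and Section 11.3.2 stops drug without stating exit. The accurate description is that functional testing after a permanent stop is not provided for.

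**A reader might infer that a link between loss and outcome could never be examined.** That is also too strong. A boy lost after Month 3 has a Month 3 100M. Table 3 lists the 100M as standard of care, and Section 11.3.4 lets the team request clinical notes, so some functional data may exist. Such a check would be partial and is not assured. The three-time-point repeated measures ANOVA in Section 13 does not settle it either, since a classical version needs complete data.

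**Analysing boys who completed treatment is defensible.** The synopsis objective concerns six months of treatment, which can be read as on-drug or as-assigned, and step 5 shows that off-drug testing can itself mislead. This stands, and is why both sets should be reported rather than one replacing the other.

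**It is a pilot, and drop-out is already allowed for.** The allowance protects power, not against bias. Section 5.1 also says the trial will answer the efficacy question directly.

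**Conclusion.** The point holds as a cheap improvement. As written, the plan gives up primary-outcome data for boys who leave under 8.5 and does not say how the equivalence test treats them.

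False equivalence is about 5% to 7% with 10% loss in both arms and equal gaps. It is about 6% to 10% with one boy lost from the spironolactone arm alone, and 7% to 19% with two. It is below 5% if the lost boys do better. All of this rests on assumed gaps of 0.5 to 2 SD, a true difference at the margin, SD 7.8 and an unstated alpha taken as 0.05 per side.

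The documents do not support saying that the trial is biased towards equivalence. They show that loss may be unbalanced, not that it will be, nor that lost boys differ. The stated power is not in error.

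**What to change.** **Section 8.5.** Leave the criteria for stopping drug to the sponsor and unchanged. Amend the opening line so that meeting a criterion does not by itself end outcome assessment: the boy is still asked to attend the scheduled Month 3 and Month 6 functional tests unless consent is withdrawn. The opening line itself must change, or the section would contradict the addition.

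**Sections 9 and 11.3.2.** Reconcile the intolerance criterion in 8.5 with the prednisone substitution in Section 9, and state the trial status of a boy whose drug is stopped under 11.3.2. Which clinical rule applies is for the sponsor.

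**Section 13.** Report the equivalence test with confidence intervals on all randomized boys as assigned and on a pre-defined on-treatment set. Name the primary set before data are seen, require the conclusion to address both, and state how Month 6 values still missing are handled. Requiring both sets to meet the margin is one option. The 85% and 83% power figures are for stayers and would be lower if the on-treatment set also excludes boys who missed more than 10% of doses.

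**Cost.** An IRB modification (Section 12.2), possible re-consent from both parents (Section 16.3), a few tests in boys off drug, and one more analysis. The visits are already scheduled. Boys who miss appointments may not be recovered.
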